Study Protocol

Protocol Title:

Postpartum HIV care engagement in the context of Option B+ in Tanzania

Principal Investigator at Duke:

[name]

Principal Investigator at KCMC (Tanzania):

[name], PhD

Version

July 23, 2018

1. Research Design

Background

The goal of this study is to examine the implementation of the Option B+ protocol, whereby all HIV-infected pregnant women initiate lifelong antiretroviral therapy (ART) during pregnancy, regardless of CD4 count or clinical staging. The Option B+ approach of establishing lifelong ART for pregnant women holds great promise for improving women's long-term health and moving towards an "AIDS free generation."¹ At the same time, there have been concerns about implementation challenges, particularly with retention and adherence in the postpartum period.^{2,3} Data from multiple African settings suggest that one-third to one-half of all women who start ART during pregnancy are lost to care within six months after childbirth.⁴⁻⁸ Retention in care and sustained adherence to ART following childbirth are vital to the success of the Option B+ protocol, to ensure the viral suppression of the woman, to prevent HIV transmission to her child during breastfeeding, and to reduce the probability that she might transmit HIV to her sexual partners.⁹

This study is filling a critical void in understanding the implementation of Option B+, and will identify opportunities to strengthen programmatic efforts to support women's long-term care engagement. Using the Consolidated Framework for Implementation Research, this study examines the Option B+ protocol in the sites in Tanzania, seeking multiple perspectives (facilities, providers, patients) and using multiple methods (observations, surveys, record reviews, qualitative interviews/discussions). Taken together, these data can help to identify bottlenecks and barriers, and inform interventions to promote women's care engagement and optimal medication adherence in the postpartum period. Preliminary findings from our cohort demonstrate the need to address stigma among pregnant women navigating PMTCT services. Therefore, this study will also develop and pilot test an intervention that addresses stigma at early entry into PMTCT.

Study aims

This study is addressing four specific aims:

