Aim #1: Examine the facility-level implementation of Option B+ in several diverse care delivery sites in the Kilimanjaro region, focusing on women's HIV care engagement in the postpartum period. *Methods:* At sites within the Moshi Urban and Moshi Rural districts of the Kilimanjaro Region, we will document practices to support postpartum HIV care engagement through clinical observations; explore implementation processes and barriers through key informant interviews with health care providers (n=30); and examine retention in care outcomes through medical record reviews of all pregnant women receiving ART through the B+ protocol since the policy was implemented in February 2014 (n=512).

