A retrospective medical record review will include a review of the clinical records of all patients in antenatal care in the study clinics, who had deliveries in a two-year period, between Feb 1, 2014 (date of roll-out) and present. Data will be analyzed to first determine the proportion of pregnant women in ANC who had a documented HIV test result as part of ANC services, and of those, the number who were HIV infected (separately by new diagnoses and established diagnoses). For patients who are HIV-infected, a data extraction form will be used to merge information across the relevant clinical services (i.e., ANC, RCH, CTC). Linking patients across the three registries will be possible by linking the unique Tanzanian CTC identification number that is given to all patients upon initiation of ART. The data extracted from each setting are described in Table 2.

Table 2: Data extracted from the clinical records of HIV-infected pregnant patients

[figure not shown]
ANC	Socio-demographics HIV testing history Counseling exposure ART initiation Engagement in care
RCH	Delivery data Counseling exposure Engagement in care Referral to CTC
CTC	Linkage to CTC (ever, date, location) Counseling exposure Engagement in care Viral load

Phase 5: Development of the *Maisha* Intervention

Procedure: Intervention development will begin during the qualitative procedures described in Phase 3, which will allow for an iterative process where new data collection builds upon what has

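### The Aim 1 record review selects women by delivery, which drops women with no recorded delivery from its antenatal measures and from retention counted from ART start; its two-year window is also not fixed

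*Combined protocol and SAP*

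**What the plan says.** Two places in Section 1 define the population of the same record review.

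- Study aims, Aim #1: retention is to be examined by "medical record reviews of all pregnant women receiving ART through the B+ protocol since the policy was implemented in February 2014 (n=512". Entry is by receipt of ART under the policy; delivery is not a condition. The aim is described as "focusing on women's HIV care engagement in the postpartum period".
- Phase 4, Medical Record Review: the records are those of ANC patients "who had deliveries in a two-year period, between Feb 1, 2014 (date of roll-out) and present". Entry is by delivery.

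Phase 4 first estimates "the proportion of pregnant women in ANC who had a documented HIV test result as part of ANC services", then counts the infected women among those tested, then extracts data on infected women from the ANC, reproductive and child health (RCH) and HIV care and treatment (CTC) records. The three sources are joined by a "unique Tanzanian CTC identification number that is given to all patients upon initiation of ART". Table 2 takes ART initiation from ANC. From RCH it takes "Delivery data Counseling exposure Engagement in care Referral to CTC". From CTC it takes linkage, with date and location.

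Neither place gives start and end dates for the two years, an abstraction cut-off, a minimum postpartum follow-up or a time point for retention. Section 10 covers the pilot trial only, so nothing there settles these points.

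**The concern.** An antenatal proportion needs everyone who entered antenatal care as its denominator. If a woman must also have a recorded delivery, those who left care during pregnancy disappear from the testing step, the ART-start step and any retention counted from ART start. They are probably less often tested, started or retained than the rest, so the remaining figures would look better than the programme's performance.

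The background figures that motivate the study run from ART start: "one-third to one-half of all women who start ART during pregnancy are lost to care within six months after childbirth". A review restricted to women who delivered has a different denominator and cannot be set beside them directly.

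The loose window adds a second problem. Depending on where the two years fall, the review may include antenatal care given before the policy, or women with too little postpartum time. Aim #1 names no other quantitative source for retention, so the denominator deserves to be settled.

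**Working it through.** **Stated figure.** The plan gives n=512 without a precision target, assumed rate or power. It reads as a count of records, so there is no calculation to reproduce.

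**1. Effect of requiring a delivery.** Let R be retention among all who started ART and d the share with no recorded delivery. If none of that share was retained, retention among those selected is R / (1 - d). The documents give neither value. As an illustration, with R = 60% and d = 5% to 20% (assumptions):

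- d = 5%: 60 / 0.95 = 63%
- d = 20%: 60 / 0.80 = 75%

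This is the extreme case. If women without a recorded delivery were retained elsewhere at the same rate as the others, the bias would be nil. The same reasoning applies to the testing and ART-start proportions. It does not apply to retention measured from delivery among women who delivered.

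**2. Length of the interval.** From roll-out (1 February 2014) to this version's date (23 July 2018) is 1,633 days, or 4.47 years. A two-year window fits inside it in many positions.

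**3. Window opening on roll-out day.** Assume even deliveries over 104 weeks, delivery at 40 weeks and a first ANC visit at 16-24 weeks. That visit falls 16-24 weeks before delivery.

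- 16 / 104 = 15.4%; 24 / 104 = 23.1% of deliveries had a first visit before roll-out.
- If infected women followed the same pattern, that is 79 to 118 per 512.
- If the first visit is instead 12-20 weeks before delivery: 84 / 730 = 11.5% and 140 / 730 = 19.2%, or 59 to 98 per 512.
- Short follow-up by July 2018: none. The last delivery (31 January 2016) is 29.7 months earlier.

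**4. Window ending at abstraction.**

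- Under 6 months postpartum: 26 / 104 = 25%, or 128 per 512.
- With abstraction on 23 July 2018, the window opens on 23 July 2016. A 280-day pregnancy ending that day began on 17 October 2015, after roll-out, so no pregnancy predates the policy.
- If short follow-up were counted as retained and loss accrued linearly over 6 months (assumptions), apparent loss = p(1 - f/2) with f = 183 / 730 = 0.251. The background range of one-third to one-half would appear as 29% to 44%.

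**5. Window in the middle.** Two years that open at least 24 weeks after roll-out (19 July 2014 or later) and close at least 183 days before 23 July 2018 (by 21 January 2018) have neither edge problem on these assumptions.

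**The case against.** Aim #1 is about postpartum engagement, and women who delivered are a proper denominator for that. Every woman delivering on or after 1 February 2014 has all her postpartum time under the policy, wherever her first visit fell. This stands: selection on delivery does not by itself bias postpartum retention among women who delivered.

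On the edges, a reader might infer that the review runs from roll-out to the present and so has both faults at once. The text limits it to two years. At this version's date a two-year window cannot have both faults; they would coincide only if abstraction took place around early 2016, and the readable text gives no abstraction date. Nor does an early first visit put a woman outside Option B+, since she could start ART after roll-out in the same pregnancy. The counts per 512 are therefore illustrations, not a tally of ineligible records.

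A reader might also infer that the linkage number removes women who never started ART. The plan does not say so. Table 2 records ART initiation from ANC, so such a woman can stay in the ANC denominator with no start and no CTC record. In the Aim #1 population every woman is on ART and so has a number.

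Short follow-up can be handled by restriction or censoring, because delivery data and CTC linkage dates are extracted. Unstated dates alone are missing detail rather than bias.

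What the objection does not answer is that Phase 4 applies a delivery-selected group to an antenatal proportion, and that its population differs from the one in Aim #1.

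**Conclusion.** The point holds for the antenatal steps and for retention counted from ART start: the rule as written omits women without a recorded delivery, and the likely direction is favourable. The size cannot be derived from the documents; 60% appearing as 63-75% is a worst-case illustration with 5-20% unrecorded and none of them retained.

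The unfixed window is a secondary point. It is worth about 15-23% of deliveries at the early edge (12-19% with later first visits), or about 25% at the late edge, or neither, depending on where the two years lie. Even deliveries and the timing of the first visit are assumptions.

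The stronger conclusion, that the review does not measure retention under Option B+, is not supported. Retention among women who delivered can still be estimated once dates and follow-up are fixed. The point concerns the Aim 1 observational review only and leaves the Aim 4 pilot trial untouched.

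**What to change.** Before abstraction:

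1. Define the cohort by first ANC visit on or after 1 February 2014, taken from the ANC records already under review. Define the B+ subset by ART start on or after that date. State the closing date and the abstraction date.
2. Report testing, ART start, recorded delivery and CTC linkage as separate steps. Show no recorded delivery and no CTC number as their own categories, with outcome unknown and transfer or delivery elsewhere possible. Add a sensitivity analysis that counts them as loss; they should not be loss by default.
3. State the retention definition and time point. Report postpartum retention among women with a delivery and enough follow-up to reach it, or censor at abstraction.
4. Use one population definition in Aim #1 and Phase 4, and say which group the 512 refers to.

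If abstraction is finished, restrict by first-visit or ART-start date and by follow-up, so far as those dates were recorded. State that women without a recorded delivery were not captured and that results apply to women who delivered. A date filter cannot recover women who were never selected.

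Cost: rewording, some extra abstraction if women without deliveries are to be included, a restated n, and probably a less favourable figure. The precision lost to the date restriction is small. Removing 118 of 512 leaves 394, and the 95% half-width, 1.96 × √(p(1 - p)/n), goes from 4.1-4.3 to 4.7-4.9 percentage points for p of one-third to one-half.

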For the full pilot test of *Maisha*, female ANC patients who are interested in enrolling in the study will be orally administered the informed consent by the study researcher. Participants will then complete an interviewer-administered, structured baseline survey. The survey will include questions about demographics, social support, attitudes toward HIV and people living with HIV, HIV testing history, and mental health. Following the baseline survey, participants will be randomized to receive either the control condition (standard of care) or the intervention condition (standard of care + *Maisha*) (Figure 4).

Participants assigned to the control condition will receive the standard of care at the clinic, which includes all standard procedures related to HIV counseling.

Participants assigned to the intervention condition will receive the *Maisha* Session 1 counseling intervention (video, followed by a brief counseling session) immediately following the baseline survey, in the same private meeting space. They will then return to the waiting area to await the standard of care for the first ANC visit (which includes HIV testing). At this time, the study researcher will inform the clinic nurse that the participant is a part of the intervention condition.

Upon completion of the standard of care HIV counseling and testing, participants who are HIV-positive will be escorted by clinic nurses back to the study researcher's office to immediately complete the *Maisha* Session 2 counseling session. At the conclusion of this session, the participant will be invited and encouraged to attend a Session 3 individual counseling session at the same location 1 week later.

3 months after baseline, all HIV-positive participants (expected n=50) and a sub-set of 100 HIV-negative participants will complete a follow-up survey. The survey will explore key constructs reflecting health outcomes (HIV care engagement, adherence to ART, mental health), stigma outcomes (internalized, anticipated, and enacted stigma), and secondary outcomes (social support, partner support, intimate partner violence). This survey will be conducted in a private room and will take approximately 60 minutes.

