Immediately after the 3-month survey, a subset of 15 HIV-positive intervention participants (5 established diagnoses, 10 new diagnoses) will be invited to participate in a qualitative in-depth interview (IDI) to explore their reactions to the intervention with greater nuance. Interviews will be conducted immediately after the survey and will take an additional 60 minutes. The IDI will be conducted in Kiswahili, using a semi-structured guide. Interviews will be audio recorded with participants' permission.

At the conclusion of pilot trial participation, the research nurse will review the medical records of the 150 pilot trial participants who are selected to receive follow-up as part of the study. A structured data extraction form will be used to record key data on HIV care engagement.

2. Subject Selection

Below are the eligibility and recruitment procedures that the KCMC team will use for inclusion of participants by study phase.

[figure not shown]
Phase 1: Key Informant Interviews with Health Care Providers

Eligibility: 30 health care providers: Individuals who are employed at one of the three study clinics and are involved in the care of HIV-infected women who are pregnant or postpartum. These individuals may include nurses, counselors, physicians, data capturers, and managers.

Recruitment: For health care providers, the KCMC PI ([name]), the Duke graduate student and KCMC research nurses will conduct a brief presentation at each of the study clinics. The research nurse and the Duke graduate student will then approach providers individually to invite them to participate in a key informant interview.

Phase 2: Surveys and In-depth Interviews with female patients

Figure 4. Pilot test design
1st ANC appointment

Eligibility: 200 female patients: Women who are ≥ 18 years of age, diagnosed with HIV, prescribed ART, and pregnant at the time of enrollment are eligible to enroll. Participants may either be newly initiating ART during pregnancy, or continuing ART due to an established HIV diagnosis. To ensure the safety of participants and integrity of the data, participants will be excluded if the attending physician determines that the patient has impaired mental status.

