Eligibility: 1000 female patients: Women who are > 18 years of age, pregnant, and attending their first ANC appointments for the current pregnancy at one of the two pilot test study sites are eligible to enroll. To ensure the safety of participants and integrity of the data, participants will be excluded if the attending physician determines that the patient has impaired mental status.

Recruitment: Research staff will work with clinic staff, including the receptionist at the Reproductive & Child Health (RCH) clinic and the ANC clinic nurse-in-charge, to identify women who are eligible for the study. When a woman arrives for her ANC appointment, she is routinely asked whether this is her first clinic appointment for the current pregnancy. For all women who answer “yes” to this question, the intake nurse will inform her that there is a research study taking place and inquire whether she would like to speak to the study researcher. Those who agree will meet with the study researcher, who will explain the study, review eligibility criteria, and offer her the opportunity to participate if she chooses, following the informed consent procedures. Clinic staff will be given a small monthly stipend to compensate for the added work of identifying and referring interested clients to the study staff; they will *not* be reimbursed based on whether or not the referral is successful, so that compensation does not create undue influence on a patient’s participation in the study. Enrollment will stop when we have enrolled 50 women who are HIV infected, which we estimate will require consenting and baselining approximately 1000 women over a six month period.

Compensation: No compensation will be offered at baseline, but nutritious snacks will be given to all women taking part. Women who attend a follow-up counseling session will receive 5000 TSh (~3 USD) to cover their transportation. Women who complete a 3-month survey will receive 5000 TSh for their participation, and snacks will be offered during the assessment. Women who complete an in-depth interview will receive an additional 5000 TSh.

3. Risks and Benefits

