Potential efficacy will be examined by analyzing separate outcomes for HIV-infected and HIV-uninfected women. For HIV-infected women, we are interested in differences between conditions in health outcomes (retention in PMTCT, medication adherence, depression) and stigma (anticipated stigma, internalized stigma and HIV disclosure). For HIV-uninfected women, we are interested in differences between conditions in stigma (attitudes to PLWH and anticipated stigma), as well as willingness to test for HIV in the future. For outcomes where there is a baseline measure, mixed-effects regressions will be used to model pre-post differences within and between arms, using a time by condition model specification (time, condition, and time*condition). Individual-level random intercepts will be used to account for correlation due to repeated measurement. Using a mixed-effects regression approach leaves flexibility to control for baseline outcome values that may not be balanced between groups due to small sample size, and may improve precision of treatment effect estimation. For outcomes where there is no baseline measure, we will examine differences in means or proportions with 95% confidence intervals. If we suspect, a priori, that baseline imbalance in prognostic covariates may be an issue, we will move into a regression framework. Results across outcomes will generate parameter estimates and potential ranges of values to estimate power for a future R01. This analytic approach is consistent with best practices for analysis of pilot feasibility trials. Data analysis will be led by the KCRI statistician and DGHI postdoc. To reduce bias and ensure reproducibility of results, we will discuss analytic approaches and review syntax as a team. All outcome analysis will be reviewed by an external statistician with study condition blinded (see letter from DGHI Research Design Core).

References

1. U.S. Department of State. *PEPFAR blueprint: Creating an AIDS-free generation*. Washington: U.S. Department of State; 2012.
3. Bateman C. Much ado over the new South African PMTCT guidelines. *S. Afr. Med. J.* Apr 2013;103(4):218-221.

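### Does the pilot RCT need stratified randomisation and a fixed adjustment rule for its 50 HIV-infected women?

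*Combined protocol and SAP*

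**What the plan says.** Aim #4 plans 150 women: 25 HIV-infected and 50 HIV-uninfected per arm. On allocation, the Phase 6 procedure gives only the timing: "Following the baseline survey, participants will be randomized to receive either the control condition (standard of care) or the intervention condition". HIV testing at that visit comes after assignment and, in the intervention arm, after Session 1. The stopping rule in Subject Selection, Phase 6, is a total over both arms: "Enrollment will stop when we have enrolled 50 women who are HIV infected", expected to take about 1000 women at two clinics.

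The infected group mixes diagnosis types. The interview subset is drawn as 15 "HIV-positive intervention participants (5 established diagnoses, 10 new diagnoses". The baseline survey covers, among other things, "attitudes toward HIV and people living with HIV, HIV testing history, and mental health".

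Section 10, Statistical analysis, uses a mixed model for outcomes with a baseline measure. For the others it reports differences in means or proportions with 95% confidence intervals, and adds: "If we suspect, a priori, that baseline imbalance in prognostic covariates may be an issue, we will move into a regression framework". The purpose is stated as "Results across outcomes will generate parameter estimates and potential ranges of values to estimate power for a future R01". As a safeguard, "All outcome analysis will be reviewed by an external statistician with study condition blinded", and the team also reviews analysis code together.

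**The concern.** Two things look unfinished.

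First, women are randomised before their HIV result is known and enrolment stops on a total. The 25/25 split is therefore an expectation, and neither clinic nor diagnosis type is balanced by any described device. In 50 women, either factor could differ noticeably between arms.

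Second, the regression sentence is hard to apply literally. Chance imbalance cannot be known before allocation, and no covariate or threshold is named. Two analysts could report different headline numbers from the same data. Retention in PMTCT and ART adherence are probably affected: a newly diagnosed woman enters care after the baseline survey and so has no baseline value (the plan does not list these outcomes, so this is a reading of it).

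At stake is whether the exploratory estimates carried into the later grant depend on an unrecorded choice. The feasibility and acceptability aims are not touched.

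**Working it through.** **Inputs from the document.** 25 + 25 + 50 + 50 = 150, as stated. 50 infected in about 1000 enrolled is 5%. Two clinics. Allocation 1:1, implied by the arm sizes. The plan gives no power calculation for the pilot, so there is no sample-size figure to reproduce.

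**Assumptions (not in the document).** Retention 67% or 80%; established share 30% to 70%; retention gap between diagnosis groups 10 to 30 points.

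**1. Arm split.** Under Binomial(50, 0.5), P(25/25) = 0.112, the central 95% range is 18 to 32, and a split of 20/30 or worse has probability 0.20. Blocks of 4 that ignore HIV status give almost the same result (0.115, 18 to 32). Cost in standard error relative to 25/25:
- 20/30: √[(1/20 + 1/30)/(2/25)] = 1.021
- 18/32: √[(1/18 + 1/32)/(2/25)] = 1.042

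So 2% to 4%, with no bias.

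**2. Mix of diagnosis types.** The arm difference in established share q has SD ≈ √[q(1−q) × 2/25]. For q = 0.5 this is √0.0200 = 0.141; for q = 0.3 or 0.7 it is √0.0168 = 0.130. Simulation with random arm sizes gives 0.143 and 0.131. A difference of 20 points or more occurs in 13% to 17% of trials. Such a difference moves the raw estimate by 0.20 × gap: 2 points at a gap of 10, and 6 points at a gap of 30.

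**3. Precision of the raw difference.** The half-width is 1.96 × √[2p(1−p)/n].

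| n per arm | p = 0.80 | p = 0.67 |
|---|---|---|
| 25 | 22.2 points | 26.1 points |
| 20 | 24.8 points | 29.1 points |

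The movement in step 2 is part of this sampling variation, not an addition to it.

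**4. Raw versus adjusted in the same 50 women** (linear regression on arm, clinic and diagnosis type; half established). Over gaps of 10 to 30 points, the median absolute difference is 1.4 to 2.9 points, the 90th percentile 4.5 to 8.3 points, and it reaches 5 points in 8% to 28% of trials. The upper ends need the 30-point gap.

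**5. What adjustment gains.** Diagnosis type explains q(1−q) × gap² / [p(1−p)] of the outcome variance. With q = 0.5 and gap 0.30, that is 0.0225/0.16 = 14% at p = 0.80 and 0.0225/0.2211 = 10% at p = 0.67. The SE factor would be √0.86 = 0.927 or √0.90 = 0.949. Estimating two extra coefficients costs about 2%, so the net is about 0.95 to 0.97; simulation gives 0.945 to 0.965. At a gap of 10 points the net is 1.013 to 1.016, which is slightly worse. With 40 women the range runs from 1.029 to 0.958.

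**6. False-positive rate with no true effect.** Using 1.96 for both, the raw interval excludes zero in 5.9% to 6.6% of trials and the adjusted one (robust HC2 standard errors) in 5.7% to 6.3%. At least one of the two does so in roughly 7% to 8%. The adjusted rate can be brought to about 5%, but that depends on the critical value used more than on the covariates.

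**7. What stratification would gain.** With blocks of 4 by clinic and self-reported known-positive status, a 20-point mix difference falls from 13–17% of trials to 2–7% if every known-positive woman discloses, and to 8–12% if half do. P(25/25) reaches only 12% to 20%.

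**The case for a change.** The best case for a change is that it is cheap and that the plan's own structure invites it. The sponsor treats diagnosis type as meaningful: it sets interview quotas by it, and in the Phase 4 record review it counts "the number who were HIV infected (separately by new diagnoses and established diagnoses". Yet neither diagnosis type nor clinic enters the analysis section. The covariates mentioned as examples in Aim #4 (partner support, attitudes to ART, intimate partner violence) are not tied to the regression step. The blinded statistician and the code review are real protections, but they have no written rule to check against. One paragraph naming a model would settle which estimate counts.

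The textual part stands: no rule and no covariates are named. The inference that the plan must change is weaker, for four reasons.

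- The regression sentence has a sensible reading: covariates are chosen on prior prognostic grounds, before outcomes are seen, rather than by testing observed imbalance.
- Silence on sequence and strata is weak evidence here. Figure 4, the pilot design, is not shown, and Table 1 schedules a step to finalise the pilot protocol.
- New diagnoses cannot be strata, because testing follows assignment by design. The substitute, self-report, relies on disclosure; the baseline survey covers testing history but is not said to record a known positive result. It also creates very small strata in which the next allocation is easier to guess.
- Clinic stratification is reasonable practice, but no separate gain from it was shown.

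**Conclusion.** No change is needed. The missing covariate list is a gap that analysts can fill sensibly, for instance by naming clinic and diagnosis type before unblinding and showing both estimates. The absence of described strata is a fair trade-off in a trial that assigns women before testing.

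Followed as written, the plan gives unbiased exploratory estimates with intervals wide enough to carry the chance imbalance. The choice of estimator typically moves the result by 1 to 3 points, against a half-width of 22 to 26 points (25 to 29 at 20 per arm). The adjusted model is not clearly better: its standard error runs from about 2% larger to about 5% smaller, and its false-positive rate is nearly the same at equal critical values. An uneven split costs 2% to 4% in standard error, and labelling 25/25 as expected alters no result. The plan asks these outcomes for ranges to power a later trial and sets no success test on them.

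The sizes rest on the assumed retention, established share and diagnosis gap. A gap well above 30 points would make adjustment more worthwhile, but nothing in the document points to one.
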